Test plan No. 2017-2

Effects on the bioavailability of β -carotene when taken concomitantly with zinc and iron supplements

Table of Contents

Abstract of the project 4

- 1. study objective 4
- 2. scientific background 4
- 3. hypothesis 5
 - 3.1 Randomization and blinding 5
 - 3.2 Target parameters and analysis 5
- 4. study population 6
 - 4.1 Number of subjects 6
 - 4.2 Duration of the study 6
- 5. selection of subjects 7
 - 5.1 Inclusion criteria 7
 - 5.2 Exclusion criteria 7
 - 5.3 Mode of recruitment 7
 - 5.4 Informed consent of study participants 7
- 6. study medication 8
 - 6.1 Pharmacological-toxicological report 8
- 7. medication 9
 - 7.1 Dosage and mode of administration 9
- 8. study procedure 9
 - 8.1 Screening 9
 - 8.2 Hospitalization 9
 - 8.3 Nutrition 9
 - 8.4 Documentation 10
 - 8.5 Trial conduct 10
 - 8.6 Methods 11
- 9 Precautionary measures / discontinuation criteria 12
 - 9.1 Risk-benefit assessment 12
 - 9.2 Adverse events 12
 - 9.3 Serious Adverse Events and Serious Unexpected Side Effects 12
 - 9.4 Discontinuation criteria 13
 - 9.4.1 Discontinuation of the study in one subject (drop-out) 13
 - 9.4.2 Discontinuation of the entire study 13
- 10 Data collection and analysis 13
- 11 Modifications of the study plan 13
- 12 Ethical and legal issues 13
 - 12.1 Legal basis 13
 - 12.2 Vote of the Ethics Committee 14
 - 12.3 Documentation, archiving and data protection 14 13 Signatures Error! Bookmark not defined.
- 14. literature 14

List of abbreviations

ADR Adverse Drug Reaction AE Adverse Event AUC Area-under-the-curve BMI Body Mass Index FDA Food and Drug Administration, U.S. Food and Drug Administration GCP Guidance on Good Clinical Practice HPLC High-pressure liquid chromatography RDA Recommended Daily Allowances SAE Serious Adverse Event SOP Standard Operating Procedure UE Adverse Event Abstract of the project

Title:

Effects on the bioavailability of β -carotene when taken concomitantly with zinc and iron supplements.

1. study objective

The objective of this study is to investigate the effect of concurrent intake of zinc or iron supplements on the bioavailability of β -carotene. The proposed trial is a purely scientific controlled, randomized, double-blind, prospective nutritional study.

2. scientific background

Iron, zinc, and vitamin A deficiencies are global public health problems and particularly affect pregnant and lactating women and children, who are especially vulnerable during the so-called 1000-day window, the period from conception to the second birthday. According to the Global Nutrition Report (2015), 29% of women of childbearing age worldwide are anemic due to iron deficiency, 15% of newborns have low birth weight, and 164 million children under the age of five are developmentally inhibited, which are signs of zinc deficiency. The situation is worse in developing countries, where an estimated 50% of pregnant women and 40% of preschool children are anemic (WHO, 2016). A recent summary analysis showed an increase in the prevalence of vitamin A deficiency in sub-Saharan populations from 45% in 1991 to 48% in 2013 (Stevens et al., 2015). These deficiencies are often treated in vulnerable populations through administration of supplements, increased dietary intake, and dietary modification. While vitamin A deficiency is increasingly treated by switching to a diet rich in β-carotene (provitamin A), severe zinc and iron deficiencies are still largely treated with supplements. Taking zinc supplements can greatly reduce the frequency and incidence of diarrhea in children under five years of age (IOM, 2001), and iron supplementation is still the preferred treatment for iron deficiency anemia (IDA) (WHO, 1998).

Since there is usually a simultaneous deficiency of vitamin A, iron and zinc, a combination of these micronutrient supplements is often recommended. However, in vitro studies suggest that intestinal absorption of β -carotene may be inhibited by iron and zinc (Bengtsson et al., 2009; Biehler et al., 2011). Fat-soluble β -carotene, in order to be absorbed in the small intestine, must be incorporated into so-called mixed micelles under the action of bile salts. Caco-2 cells incubated with micellated β -carotene and different concentrations of iron absorbed on average

Version 4 vom 2. Oktober 2017

22% less β -carotene in the presence of iron (Bengtsson et al., 2009). Another study examined the effects of different concentrations of magnesium, calcium, iron, and zinc on the ability to form micelles and uptake β -carotene in Caco-2 cells (Biehler et al., 2011). The micellation of β -carotene and its uptake into Caco-2 cells decreased with increasing concentrations of the minerals. Iron and zinc had a much stronger inhibitory effect than calcium and magnesium. In both studies, the authors attributed the decreased absorption of β -carotene to an interaction of iron with bile salts and a resulting decreased micellation.

Experiments performed in our laboratory with Caco-2 cells confirm the results of the above studies, as we also measured a dose-dependent reduction in micellation of β -carotene with increasing iron concentration.

To the best of our knowledge, no human studies have been performed to determine the influence of iron and zinc supplements on the bioavailability of β -carotene. However, these are of great importance and relevance because in vitro systems are not dynamic and cannot adequately model the influence of minerals on β -carotene bioavailability. For example, it is possible that the continuous secretion of bile salts in vivo may compensate for precipitation by minerals and thus the reduction in absorption.

3. Hypothesis

Based on the in vitro experiments described above (see 2), which observed reduced micellization of β -carotene in the presence of iron and zinc, we will test the hypothesis that when β -carotene is taken simultaneously with iron or zinc, its bioavailability is reduced in healthy subjects.

3.1 Randomization and Blinding

To avoid systematic errors and otherwise influencing the results, the study will be randomized and double-blinded. Randomization and blinding will be done before the start of the study and will be performed by a staff member who is not actively involved in the study. For this purpose, the samples obtained will be randomly numbered and the key to unblinding, i.e., the assignment of the randomly generated sample numbers to the specific samples (identified by time of sampling and type of intervention), will be stored in sealed envelopes in two different locations in locked cabinets.

Subjects receive the different preparations (15 mg β -carotene and placebo, 15 mg β -carotene with 25 mg iron, or 15 mg β -carotene with 30 mg zinc) in capsules in random order. Analysis of plasma samples was also randomized and blinded to prevent inadvertent influence of the experimenter on the results. Unblinding of the samples for statistical analysis of the data is done only after all biochemical analyses have been completed.

3.1 Target parameters and evaluation

The bioavailability of β -carotene is determined via the measured plasma and chylomicron concentrations by HPLC (see 8.6 Methods). For this purpose, ultracentrifugation is used to isolate the chylomicron fraction and extract β -carotene. Pharmacokinetics for plasma and chylomicron fraction are calculated using the area under the concentration-time curve. This quantity can be used to quantify the bioavailability of β -carotene in comparison between single and combined intakes. Statistical analysis is performed using one-factor analysis of variance.

4. study population

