4.1 Number of subjects

The required power for the study will be calculated based on the area under the plasma concentration-time curve (AUC). Study power is calculated based on the following formula: n > F (σ /d)2, where n = number of subjects, σ = standard deviation of the dependent primary outcome measure, d = difference between control and treatment classified as significantly different in the literature. The corresponding F-values can be found in the table below; for the planned study, P < 0.05 and 90% power are assumed, resulting in an F-value of 10.51 (Scales & Rubenfeld 2005).

	Power			
Significance level (P-value)	80%	90%	95%	99%
0.100	6,18	8,56	10,82	15,77
0.050	7,85	10,51	12,99	18,37
0.025	9,51	12,41	15,10	20,86
0.010	11,68	14,88	17,81	24,03

F-value Table:

In a comparable study by (Goltz et al. 2013), an AUC of 22.6 \pm 7.6 [nmol*L-1*h] could be determined after intake of 20-30 mg β -carotene (n=6). This results in a mean value of 22.6 nmol*L-1*h and a standard deviation of 7.6 nmol*L-1*h. A reduction of bioavailability by more than one third would represent a biologically relevant effect, which is why a significant difference of rounded up 35%, corresponding to 7.9 nmol*L-1*h, is used for the calculation in this study. Thus, n > 10.51 x (7.6/7.9)2 results in a number of at least 9.7, rounded up to 10 subjects. To allow for a balanced experimental design in which all permutations of the timing of the interventions occur in equal numbers, a total of 12 healthy males aged 18-45 years will be recruited for this study. Females will be excluded from the study because the menstrual cycle affects blood concentrations of carotenoids (Forman et al. 1998).

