8.5 Experimental procedure

Subjects are considered to be enrolled in the study if all inclusion criteria have been met during screening (see section 5.1), none of the exclusion criteria (see section 5.2) are present and the subjects have given their written consent to participate in the study.

On the evening before the intervention, subjects will receive a standardized meal and a standardized snack for consumption between dinner and 10 pm. Subjects will be asked to drink only water and consume no other food after 10 pm and until the intervention on the day of the trial. On the morning of the trial day, subjects will receive a single oral dose of 15 mg β -carotene plus placebo, 15 mg β -carotene combined with 25 mg iron (FeSO4), or 15 mg β -carotene combined with 30 mg zinc (ZnSO4) after breakfast. Standardized meals will be served to study participants throughout the day of the intervention. Blood samples will be collected at baseline (0 h) and 1, 2, 3, 4, 5, 6, 7, 8, 9, and 10 h after ingestion of the study drugs (11 blood samples). A total of approximately 120 mL of blood will be collected per intervention.

As the study is a cross-over study with three arms, after each 1-week washout period, the same experimental procedure is performed in random order with one of the remaining study preparations each time.

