9.4.2 Termination of the entire study

If the suspected case of a serious unexpected adverse reaction occurs during the human study after taking 15 mg β -carotene plus placebo, 15 mg β -carotene with 25 mg iron (FeSO4), and 15 mg β -carotene with 30 mg zinc (ZnSO4), the study will be terminated at any time for the benefit and in the interest of the subjects. In this case, the Ethics Committee would be informed immediately.

10 Data collection and analysis

Statistical analysis will be performed by the study coordinator. Bioavailability will be determined by the area under the curve (AUC), maximum plasma concentration (Cmax), and time to reach Cmax (Tmax) of β -carotene. Significant differences between interventions will be determined using GraphPad Prism 6.0 software using one-factorial analysis of variance for repeated measures.

11. amendments to the protocol.

The applicants are aware that the vote of the Ethics Committee covers only the information contained in the application and does not include extensions and changes to the research proposal made at a later date. The applicants are aware that in case of changes, a protocol annex is required, which must be signed by the study directors, and that all protocol changes must be reported to the Ethics Committee. The applicants are aware that a new vote of the Ethics Committee must be obtained for protocol changes that are not exclusively formal in nature and that contain changes relevant to the study participants. Potential changes in study conditions would be brought to the attention of study participants during the informed consent process.

12 Ethical and legal issues

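### The one-factor ANOVA leaves visit-to-visit change and drift in fasting β-carotene in the error term, although a 0 h sample is drawn at every visit

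*Combined protocol and SAP*

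**What the plan says.** Section 3.1 (Target parameters and evaluation) gives the outcome in one sentence: "Pharmacokinetics for plasma and chylomicron fraction are calculated using the area under the concentration-time curve". Section 10 adds the other parameters: "Bioavailability will be determined by the area under the curve (AUC), maximum plasma concentration (Cmax), and time to reach Cmax (Tmax) of β -carotene". It compares treatments "using one-factorial analysis of variance for repeated measures"; section 3.1 names a one-factor ANOVA without the repeated-measures qualifier. Neither section mentions baseline correction, a covariate or a period term.

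Section 8.5 begins its sampling schedule with "Blood samples will be collected at baseline (0 h", followed by hourly samples to 10 h, and repeats the same procedure at all three visits. Section 4.2 puts a one-week washout before each visit, about three weeks in all, and section 6.1 describes the washout diet as low in carotenoids.

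Section 4.1 sizes the trial on plasma AUC, with σ defined as the "standard deviation of the dependent primary outcome measure". From a cited study it takes the planning values: "This results in a mean value of 22.6 nmol*L-1*h and a standard deviation of 7.6 nmol*L-1*h". It does not say whether that AUC was baseline-corrected or what time window it covered. It chooses 12 subjects for a design "in which all permutations of the timing of the interventions occur in equal numbers".

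**The concern.** β-carotene is present before dosing, so a raw AUC over 10 h contains about ten hours of the fasting level. If that level is constant within a subject, the repeated-measures model removes it. Two other parts are not removed:

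- a subject's own change in fasting level from visit to visit;
- a shift common to all subjects over successive weeks of a low-carotenoid diet.

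Both go into the residual against which iron and zinc are tested. With 12 subjects and a target difference equal to only 0.79 nmol/L averaged over 10 h, modest fasting variation could matter. The 0 h sample that would measure it is already collected, but the plan gives it no role beyond its place on the curve.

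**Working it through.** **The plan's own figure.** Inputs from section 4.1: F = 10.51 (two-sided 0.05, 90% power), σ = 7.6, d = 35% of 22.6 = 7.91, used as 7.9. Then n > 10.51 × (7.6/7.9)² = 10.51 × 0.9255 = 9.73, so 10. This agrees with the plan's 9.7 and 10. The formula is the paired form, so 7.6 acts as the SD of a within-subject difference.

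**Scale.** If the planning AUC covers the 10 h of section 8.5, the target is 7.9/10 = 0.79 nmol/L (0.99 over 8 h, 0.66 over 12 h).

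**Visit-to-visit variation, by formula.** Assume that 7.6 contains no baseline variation and that the fasting level has SD s between visits, carried over 10 h. The SD of a paired difference in total AUC is √(7.6² + 2(10s)²). Paired t, n = 12, two-sided 0.05:

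| s (nmol/L) | SD of difference | Power |
|---|---|---|
| 0 | 7.60 | 90.5% |
| 0.25 | √(57.76 + 12.5) = 8.38 | 84.4% |
| 0.5 | √(57.76 + 50) = 10.38 | 67.1% |
| 1.0 | √(57.76 + 200) = 16.05 | 34.4% |

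**Comparison of models, by simulation.** 12 subjects, six orders twice each, one treatment lowered by 7.9, unadjusted contrast with control, within-subject SD 7.6/√2 = 5.37, 40,000 runs per row. Total AUC = incremental AUC + 10b + 0.5e and observed 0 h value = b + e, where b is the visit's fasting level (SD s) and e the error of the 0 h sample (0.5 h is its trapezoidal weight). Error df: 36 − 12 − 2 = 22 for one-factor, 20 with period, 19 with period and the 0 h covariate. Power in %:

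| s | SD of e | One-factor | + period | + period + 0 h |
|---|---|---|---|---|
| 0 | 0.25 | 93.1 | 92.9 | 91.2 |
| 0.25 | 0.25 | 87.6 | 87.3 | 88.4 |
| 0.25 | 1.0 | 87.1 | 86.8 | 85.9 |
| 0.5 | 0.25 | 70.9 | 70.5 | 86.9 |
| 0.5 | 0.5 | 71.3 | 70.7 | 80.5 |
| 0.5 | 1.0 | 71.3 | 71.0 | 74.4 |
| 0.25, drift 0.5 per visit | 0.25 | 69.0 | 87.3 | 88.8 |

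The one-factor column starts at 93% rather than 90.5% because its error is pooled over three treatments (22 df against 11). In the drift row nearly all the recovery comes from the period term.

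**False positives, no true effect.** With s = 0.5, error 0.25 and no drift: 4.9% one-factor, 5.0% covariate model. With drift 0.5 per visit (s and error 0.25): 1.1% one-factor, 5.1% covariate model. Drift therefore makes the planned test conservative, not anti-conservative.

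**If 7.6 already contains the baseline variation.** Then s ≤ 7.6/(10√2) = 0.54, and the within-subject SD of the incremental part is √(7.6²/2 − (10s)²). Without drift, one-factor power stays at about 93%. The covariate model gives about 91% to 92% at s = 0.1, about 92% at s = 0.25 with 0 h error 1.0, and up to 99% at s = 0.4 with error 0.25.

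**The case against.** The strongest reply is that the planned analysis is sound. It removes a stable fasting level, and all orders are used equally. Diet restriction, standardized meals (section 8.3), water only after 10 pm (section 8.5) and one-week washouts all limit fasting variation. Every value of s, 0 h error and drift above is assumed. Without drift the period term gains nothing (93.1% against 92.9%). The covariate lowers power slightly when fasting variation is small: 93% to 91% at none, and 87.1% to 85.9% at s = 0.25 with 0 h error 1.0. Its benefit also fades as 0 h error grows: at s = 0.5 and error 1.0 it recovers about 3 of some 22 lost points. All of this stands. It limits the point to a cheap improvement of uncertain size.

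Three stronger readings are tempting, and the documents do not support them.

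- A reader might infer that the outcome is undefined and will be chosen after the results are seen, because "Unblinding of the samples for statistical analysis of the data is done only after all biochemical analyses have been completed". The plain reading of sections 3.1 and 10 is raw AUC and raw Cmax; no increment or subtraction is mentioned. An explicit statement is still worth having, because nothing ties unblinding to one.
- A reader might infer that the treatment estimates are biased. With 12 completers and equal orders, each treatment occurs four times in each period, so an additive drift cancels. Sections 9.2 and 9.4.1 provide for removing subjects and no replacement rule is stated, so the cancellation would no longer be exact if the orders became unequal.
- A reader might infer a loss of 50 points or more. That needs s = 1.0 (37% for one-factor against about 88% for simple subtraction at error 0.25). This s exceeds the whole target effect, and it is impossible if 7.6 already contains the baseline variation (bound 0.54).

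**Conclusion.** The point holds as a matter of precision and should be fixed. The planned model leaves visit-to-visit change and common drift in fasting β-carotene in the error term, although the data to deal with both are collected. It does not follow that the trial is underpowered. That depends on what the SD of 7.6 contains, which section 4.1 does not say.

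The illustrated sizes are 69% to 87% for a period term under a drift of 0.5 nmol/L per visit, and 71% to 87%, 80% or 74% for the covariate at s = 0.5 with 0 h error SD 0.25, 0.5 or 1.0. They rest on 7.6 being a paired-difference SD free of baseline variation, on a 10 h window, and on assumed variation and drift. They concern plasma AUC only; the documents give no figures from which to do the same for Cmax or the chylomicron fraction. Confidence is high that the terms are absent and only moderate that the gain is material.

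**What to change.** In section 3.1 (Target parameters and evaluation) and section 10, before unblinding, state:

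> The primary outcome is plasma β-carotene AUC0-10h (total, linear trapezoidal), analysed in a linear model with subject (fixed), period, treatment and the same visit's 0 h concentration as covariate. Chylomicron AUC0-10h and Cmax are analysed the same way as secondary outcomes. Incremental AUC0-10h and Cmax minus C0 (signed values) are supporting results.

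Plasma AUC is named as primary because section 4.1 bases the power on it. Incremental AUC0-10h is the total minus 10 h times the 0 h value. It is kept as supporting because subtraction carries the error of a single 0 h sample in full: its simulated power is 88% at error SD 0.25, 73% at 0.5 and about 40% at 1.0.

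In section 4.1, state whether the planning AUC of 22.6 ± 7.6 was baseline-corrected and over what time window.

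Cost: no new sample or visit. Error degrees of freedom fall from 22 to 19 (two for period, one for the covariate), with at most about 2 points of power lost if the baseline does not vary. At the very least, state total or incremental before unblinding, which costs nothing.

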4.1 Number of subjects

The required power for the study will be calculated based on the area under the plasma concentration-time curve (AUC). Study power is calculated based on the following formula: n > F (σ /d)2, where n = number of subjects, σ = standard deviation of the dependent primary outcome measure, d = difference between control and treatment classified as significantly different in the literature. The corresponding F-values can be found in the table below; for the planned study, P < 0.05 and 90% power are assumed, resulting in an F-value of 10.51 (Scales & Rubenfeld 2005).

	Power			
Significance level (P-value)	80%	90%	95%	99%
0.100	6,18	8,56	10,82	15,77
0.050	7,85	10,51	12,99	18,37
0.025	9,51	12,41	15,10	20,86
0.010	11,68	14,88	17,81	24,03

F-value Table:

In a comparable study by (Goltz et al. 2013), an AUC of 22.6 \pm 7.6 [nmol*L-1*h] could be determined after intake of 20-30 mg β -carotene (n=6). This results in a mean value of 22.6 nmol*L-1*h and a standard deviation of 7.6 nmol*L-1*h. A reduction of bioavailability by more than one third would represent a biologically relevant effect, which is why a significant difference of rounded up 35%, corresponding to 7.9 nmol*L-1*h, is used for the calculation in this study. Thus, n > 10.51 x (7.6/7.9)2 results in a number of at least 9.7, rounded up to 10 subjects. To allow for a balanced experimental design in which all permutations of the timing of the interventions occur in equal numbers, a total of 12 healthy males aged 18-45 years will be recruited for this study. Females will be excluded from the study because the menstrual cycle affects blood concentrations of carotenoids (Forman et al. 1998).

4.2 Duration of the study

The duration of the study is approximately 3 weeks per subject and includes 3 interventions, each preceded by a 1-week washout period. The three interventions each consist of a single oral administration of 15 mg β -carotene with placebo, in combination with 25 mg iron (FeSO4), or in combination with 30 mg zinc (ZnSO4).

5. selection of subjects

5.1 Inclusion criteria

Healthy, consenting males aged 18 to 45 years are sought for the study. A prerequisite for participation is that the small blood count, parameters of liver and kidney function, lipid metabolism, inflammatory markers, blood pressure and body mass index (BMI) are within the normal range.

5.2 Exclusion criteria

Subjects will not be included in the study should at least one of the following exclusion criteria be present: Use of medication, previous myocardial infarction, addiction, malignant disease, diabetes mellitus, dementia, arterial hypertension, smoking, increased alcohol consumption, use of multivitamin tablets or food supplements, extreme physical stress (>5 hours of exercise

Version 4 vom 2. Oktober 2017

per week) and in case of a known intolerance/hypersensitivity to the preparation (β -carotene, iron, zinc or fillers used).

Subjects enrolled in another study during the same time period or who have participated in another clinical trial within the previous 3 weeks will not be enrolled in the study.

